11.1.1. Study Drug Administration Considerations

As described in the [EXPAREL Full Prescribing Information](#) (November 2018), no agents are to be admixed with EXPAREL (e.g., epinephrine, dexamethasone, clonidine) other than bupivacaine HCl. Lidocaine and other local anesthetics are not permitted to be locally administered during the surgery because they are known to interact with EXPAREL, resulting in the displacement of bupivacaine and elevated plasma levels. When a topical antiseptic is applied to the surgical site, the solutions should not be allowed to come in contact with each other (e.g., the area must be dry

before EXPAREL is administered). Upon discovering use of any prohibited therapy and/or medication during or after surgery, the investigator should document all events that led to the deviation, write a note to file, and notify the Pacira Medical Monitor accordingly.

EXPAREL may not be administered to a subject if the vial has been open for more than 4 hours. In order to prevent EXPAREL from settling, gently inverting and re inverting the syringe prior to administration is recommended.

The maximum dosage of EXPAREL should not exceed 266 mg.

11.1.2. Bupivacaine HCl Administration Considerations

Given the potential risk of severe adverse effects associated with bupivacaine HCl, the study sites must be equipped to manage subjects with any evidence of cardiac, neurological, or respiratory toxicity.

Bupivacaine HCl is contraindicated in subjects with known hypersensitivity to amide-like local anesthetics. Caution must be exercised to prevent incidental intravenous administration of bupivacaine during block placement.

11.2. Identity of the Investigational Products

11.2.1. Description of EXPAREL

EXPAREL (bupivacaine liposome injectable suspension) is formulated as a sterile, non-pyrogenic, white to off-white, preservative-free homogenous suspension of bupivacaine encapsulated into multivesicular liposomes (DepoFoam drug delivery system). Bupivacaine is present at a nominal concentration of 13.3 mg/mL. For this study, EXPAREL will be provided in 20-mL, 1.3% (13.3 mg/mL) single-use, clear glass vials. EXPAREL vials should be stored refrigerated at 2°C to 8°C (36°F to 46°F).

11.2.2. Description of Reference Product

The reference product is 0.25% bupivacaine HCl administered via combined sciatic (in popliteal fossa) and adductor canal nerve block.

11.3. Method of Assigning Subjects to Treatment

11.3.1. Randomization Scheme

This is a randomized study. Cohort 1 will enroll approximately 60 total subjects undergoing bunionectomy surgery randomized 1:1:1 in the EXPAREL arm, EXPAREL admixed with 0.25% bupivacaine HCl arm (“admix” arm), and bupivacaine HCl arm.

Cohort 2 will enroll approximately 60 total subjects undergoing distal lower extremity surgery, 20 subjects in each treatment arm; EXPAREL arm, EXPAREL admix arm, and bupivacaine HCl arm. Subjects will be randomized 1:1:1 to treatment groups, by stratifying by surgery grouping. The randomization code will be generated by a centralized randomization system, which will also be used to communicate subject randomizations to study sites. All randomized subjects will have

both a unique subject identifier and a unique randomization code. No subject or randomization code identifiers will be reused once assigned.

11.3.2. Randomization Procedures

Once a subject is identified as being qualified for the study in accordance with the eligibility criteria (see [Section 10.1](#) and [Section 10.2](#)), the investigator or designee will obtain a randomization assignment on the day of surgery. In rare cases, if a subject has an early morning surgery and there would not be enough time to obtain study drug from the pharmacy, sites will be permitted to randomize the subject the day before the surgery (after contacting the subject the day before surgery to confirm eligibility details). The e-diary may be activated during the screening period in order to perform set-up and training, but no data entry may occur in the e-diary before the day of surgery. The subject will be considered randomized into the study once the study treatment assignment is assigned.

11.3.3. Replacement of Subjects

Subjects who withdraw from the study before receiving study drug may be replaced. Once a subject number is assigned, subject numbers will not be reused; subjects enrolled to replace those who withdraw will be assigned a unique subject number and randomized to treatment according to the procedures outlined above. Subjects who are randomized but are withdrawn from the study before receiving study drug or do not undergo the surgical procedure may be replaced. Additionally, subjects may be replaced if insufficient and/or incomplete data are noted on PK profiles or efficacy endpoints.

11.4. Selection of Doses in the Study

During the clinical development of EXPAREL, single doses ranging from 2 mg to 665 mg have been safely administered via various routes. Pharmacokinetic studies have shown that because EXPAREL releases bupivacaine gradually as the lipid structure breaks down, administration of EXPAREL 266 mg results in a maximum plasma concentration equivalent to that seen with standard bupivacaine HCl 100 mg. Clinical studies have shown that, for wound infiltration, a total dose of 266 mg (20 mL) of EXPAREL is safe and efficacious. Based on this experience, the FDA-approved marketed dose of 266 mg was deemed appropriate for this study.

As a part of the clinical developmental program, a pilot dose-escalation study (402-C-122) evaluating the PK, PD, and safety of EXPAREL as a sciatic nerve block in the popliteal fossa in subjects undergoing bunionectomy was conducted. The preliminary results for this study showed that compared to the EXPAREL 266 mg or 133 mg admixed groups, EXPAREL 266 mg had similar NRS pain scores, opioid consumption, and onset and duration of block, but produced lower PK concentrations of bupivacaine HCl. Thus, a total dose of 266 mg was deemed appropriate for the current study population administered in two halves as 133 mg EXPAREL in each of the sciatic and saphenous nerve blocks.

11.5. Blinding

11.5.1. Unblinding Procedures

Blinded study personnel should not be unblinded to the subject treatment assignments during the study. The investigator will have the ability to unblind a subject through the randomization system if it is felt that subject safety warrants such unblinding. However, if possible, the investigator should discuss the safety issues with the Pacira Medical Monitor before attempting such unblinding. Any unblinding will be documented through immediate notification of the Pacira study team and the investigator within the interactive response technology system used for randomization. The reason for unblinding will be documented. Any accidental unblinding events (i.e., through mishaps in the operating room or miscommunication among study staff) must be reported to Pacira immediately. Any unblinding performed through the randomization system will be recorded as a transaction, and the appropriate study personnel will be notified that such a transaction occurred. Any incidence(s) of unblinding will be noted in the clinical study report with a full discussion of the events leading to the decision to unblind.

11.5.2. Blinding Procedure

EXPAREL, EXPAREL admixed with 0.25% bupivacaine HCl, and 0.25% bupivacaine HCl are visually distinguishable; therefore, to maintain the double-blind study design, the individuals preparing and administering study drug, or transporting unblinded drug will not be allowed to perform any of the study assessments after randomization (with the possible logistical exception of drawing blood in the operating room (OR) to be processed by blinded staff for the PK assessments) or reveal the assigned study treatment to any other members of the study team at any time. Additionally, efforts will be made to prevent the subject from observing the study drug syringe. Syringes containing study drug will need to be gently inverted several times to re-suspend any settling of the study drug that may have occurred prior to administration. The administration of study drug will be recorded using the minimal amount of information necessary to avoid unblinding staff who will be participating in blinded procedures.

Staff members conducting study-specific, postsurgical assessments and the subjects will remain blinded to the assigned treatment throughout the study in part by not being present during the administration of the nerve blocks.

If a subject experiences an SAE, Pacira will not automatically unblind the subject's treatment, unless it is necessary to manage treatment of the SAE. Expedited SAEs will be unblinded by Pacira for regulatory reporting purposes.

At each site, only the designated unblinded pharmacist will receive unblinded randomization assignments; the designated unblinded pharmacist or administrator will be responsible for preparing study drug.

No crossover will be permitted between the blinded and unblinded study site personnel throughout the study. The assignment of site monitors will also be segregated. Blinded monitors will review CRFs, clinic charts, and all other study-related documents that do not disclose the allocation of study treatment. Care should be taken in recording and review of OR records to not record information in an unblinded fashion. Pharmacy or any other clinic records providing unblinded

information (e.g., randomization, study drug preparation, study drug accountability, study drug administration) will be reviewed by specialized unblinded monitors who will notify Pacira of treatment noncompliance.

The independent review committee conducting the interim analyses will not be blinded to the study drug.

Additional details are outlined in the study-specific Blinding Plan.

11.6. Prior and Concomitant Therapy and Medications

Concomitant medications will be coded using the World Health Organization Drug Dictionary. The number and percent of subjects taking concomitant medications will be tabulated for each treatment group by Anatomic Therapeutic Chemical class and preferred terms.

11.6.1. Prior to Study Drug Administration

Permitted Prior Medications and Therapy:

- Low-dose aspirin for cardioprotection
- 1 to 2 mg of midazolam (Versed)

Restricted Prior Medications and Therapy:

- Systemic glucocorticosteroids and neuromodulating agents (e.g., gabapentin, pregabalin [Lyrica], duloxetine [Cymbalta], etc.)
- Long-acting or sustained release opioid medications and NSAIDs (except for low-dose aspirin used for cardioprotection) are not permitted within 3 days of study drug administration.
- Dexmedetomidine HCl (Precedex) use is not permitted within 3 days of study drug administration.
- No opioid medications are permitted within 24 hours of study drug administration.
- Use of an investigational product within 30 days or 5 elimination half-lives of such investigational drug, whichever is longer, prior to study drug administration, or planned administration of another investigational product or procedure during the subject's participation in this study is not permitted.
- No drugs (other than the described bupivacaine HCl admixture) are to be admixed with study drug (e.g., epinephrine, dexamethasone, clonidine).
- Lidocaine and other local anesthetics will not be permitted to be locally administered in the area of the nerve block administration other than use in a superficial cutaneous wheal for needle insertion.

11.6.2. Perioperative

Permitted Medications:

- Acceptable anesthetic techniques include general anesthesia or non-opioid sedation (except fentanyl, not to exceed 1 ug/kg unless deemed medically necessary). Neuroaxial or regional anesthesia technique (except the investigational related blocks) are not permitted.
- Single-dose administration of ondansetron or metoclopramide may be used intra-operatively for nausea/vomiting prevention.

Restricted Medications:

- Intraoperative use of opioids (except fentanyl, not to exceed 1 ug/kg unless deemed medically necessary) and ketamine will not be permitted.
- The use of dexamethasone, acetaminophen/paracetamol, ketorolac, or other NSAIDs will not be permitted preemptively or intraoperatively except for emergency use to treat an AE.
- Lidocaine and other local anesthetics will not be permitted to be locally administered in the area of the nerve block administration.

11.6.3. Post-surgery

Permitted Medications:

- Ondansetron or metoclopramide may be used for postoperative nausea and vomiting.
- Postsurgical pain medications for breakthrough pain as outlined in [Section 11.7](#).

Restricted Medications:

- No other analgesics, including fentanyl, are permitted within 96 hours after surgery.
- Patient Controlled Analgesia is not permitted.
- Dexmedetomidine HCl (Precedex) use is prohibited.
- Lidocaine and other local anesthetics will not be permitted to be locally administered in the area of the nerve block administration through POD 7.

11.7. Postsurgical Pain Medication for Breakthrough Pain

An unscheduled pain intensity assessment using the NRS (measured as “How much pain are you experiencing right now?”) must be completed immediately prior to administration of any breakthrough pain medication up to 96 hours post-surgery. All opioid and other analgesics (pain medications) administered post-surgery through POD 14 must be recorded.

Medications will be provided on an as needed (PRN) basis in relation to the breakthrough pain intensity. The intent is to use the guide below in a step-wise approach; acetaminophen or NSAIDs should be used for the initial treatment of post-surgical pain and escalation to opioids (and subsequent increased dose of opioids) should be implemented if the initial pain treatment (and initial opioid dose) is insufficient for pain relief. Opioids should not be the first choice for pain relief unless clinically indicated in the opinion of the investigator and should not be given on a schedule.

- For the initial treatment of post-surgical pain, subjects may receive either acetaminophen or NSAIDs without exceeding the maximum daily dose.
- If the initial pain treatment (acetaminophen or NSAIDs) is insufficient for pain relief, immediate release PO oxycodone may be administered in a stepwise approach:
 - Initial dose of 5 mg oxycodone may be offered;
 - If the initial opioid dose is insufficient for pain relief, 10 mg oxycodone may be offered.
- If a subject is unable to tolerate PO medication or the PO oxycodone pain relief is insufficient, IV morphine (initiated at 2 mg) or hydromorphone (initiated at 0.2 mg) may be administered.

Post discharge, the subject may be provided with a prescription for oxycodone 5 mg. The subject may take acetaminophen, NSAIDs, or the prescribed oxycodone and will be given instructions on which medication to take PRN based on their pain intensity.

11.8. Treatment Compliance

Not applicable, since study drug (EXPAREL, EXPAREL admix, or bupivacaine HCl) will be administered preoperatively by the study staff.

11.9. Accountability of Study Drug

Any shipment of EXPAREL for the study will contain an investigational drug transmittal and receipt form to assist the Investigator or designee (e.g., pharmacist) in maintaining current and accurate inventory records. At a minimum, the Investigator or designee will maintain accurate records demonstrating dates and units of drug received, lot numbers, subjects to whom drug was administered, and accounts of any drug destroyed accidentally or deliberately. The Investigator must retain vials containing used, unused, or expired study drug for return or destruction, as instructed by Pacira, following confirmation of drug accountability data by an unblinded study monitor. A record of drug return or destruction will be maintained and provided to Pacira. Inventory records must be readily available for inspection by the unblinded study monitor and appropriate regulatory authorities at any time. A copy of the inventory records, drug accountability information, and notice of return or destruction will be returned to Pacira at the end of the study. Only authorized personnel identified by the Investigator will have the ability to access and administer the study drug.

12. STUDY ENDPOINTS AND MEASUREMENTS

12.1. Efficacy Assessments

- Pain intensity measured using the NRS as “How much pain are you experiencing right now?” will be assessed:
 - Upon arrival in the Post-anesthesia Care Unit (PACU) (± 5 min)

- Every 15 minutes in the PACU (± 5 min)
- At PACU discharge (± 5 min)
- Every 6 hours from the end of surgery until 96 hours post-surgery: 6 h (± 2 h), 12 h (± 2 h), 18 h (± 2 h), 24 h (± 2 h), 30 h (± 2 h), 36 h (± 2 h), 42 h (± 2 h), 48 h (± 2 h), 54 h (± 2 h), 60 h (± 2 h), 66 h (± 2 h), 72 h (± 2 h), 78 h (± 3 h), 84 h (± 3 h), 90 h (± 3 h), and 96 h (± 3 h)
- An unscheduled NRS assessment will be obtained immediately prior to administration of any breakthrough pain medication until 96 hours post-surgery.
- Pain intensity using the NRS once daily at 21:00 (± 3 h) from POD 1 to POD 14 measured as “What was your **worst** pain in the last 24 hours?”
- Pain intensity using the NRS once daily at 21:00 (± 3 h) from POD 1 to POD 14 measured as “What was your **average** pain in the last 24 hours?”
- In addition, subject satisfaction with pain management using 1 question from the International Pain Outcome (IPO) questionnaire will be recorded at 96 hours (± 3 h) post-surgery.

Subjects will be instructed to focus all NRS pain intensity ratings on the operative ankle/foot, and not other locations where they may be experiencing pain.

The following information shall be captured for data management purposes:

- Start and end time of block
- Start and stop time of surgery
- Start and stop of PACU admission and discharge
- Date and time of health care facility admission and discharge

12.2. Efficacy Endpoints

Primary Endpoint:

- The area under the curve (AUC) of the NRS pain intensity scores from 0 to 96 hours post-surgery comparing EXPAREL to 0.25% bupivacaine HCl

Secondary Endpoints:

- Total postsurgical opioid consumption in oral morphine equivalents (OMED) from 0 to 96 hours post-surgery comparing EXPAREL to 0.25% bupivacaine HCl
- Time to first opioid consumption comparing EXPAREL to 0.25% bupivacaine HCl
- The AUC of the NRS pain intensity scores from 0 to 96 hours post-surgery comparing EXPAREL to EXPAREL admixed with 0.25% bupivacaine HCl
- The duration of the motor block EXPAREL to EXPAREL admixed with 0.25% bupivacaine HCl

12.3. Safety Assessments

- Adverse events (AEs) and SAEs will be recorded from the time of informed consent through POD 14

12.4. Safety Endpoints

- Incidence of treatment-emergent AEs and SAEs from the start of block procedure through POD 14

12.5. Pharmacokinetic Assessments (Cohort 1 only)

Blood samples for PK assessment will be obtained from the Cohort 1 subjects. A total of 17 PK samples will be collected for each subject. These samples will be obtained at predose (up to 15 min before block), 30 min (± 5 min), 45 min (± 5 min), and 1 h (± 15 min), 2 h (± 30 min), 8 h (± 30 min), 12 h (± 30 min), 24 h (± 1 h), 30 h (± 1 h), 48 h (± 1 h), 60 h (± 2 h), 72 h (± 2 h), 84 h (± 2 h), 96 h (± 3 h), 120 h (± 3 h), 144 h (± 3 h), and 168 h (± 3 h) hours from end of block procedure. (See [Table 2](#)).

12.6. Pharmacokinetic Endpoints (Cohort 1 only)

The following model-predicted PK endpoints will be determined:

- Area under the plasma concentration-versus-time curve (AUC)
- Maximum plasma concentration (C_{\max}) and time of C_{\max} (T_{\max})
- The apparent terminal elimination half-life ($t_{1/2el}$)
- Apparent clearance (CL/F)
- Apparent volume of distribution (Vd)

12.7. Pharmacodynamic Assessments (Cohort 1 only)

Pharmacodynamic assessments must be performed by trained licensed medical staff (e.g., Physician, Registered Nurse, Physician Assistant) and documented on the investigator's study delegation log. A limited number of study staff should perform the sensory/motor assessments.

Assessment of sensory functions (Light Touch Assessment and Cold Sensation Assessment):

- Sensory functions will be assessed using a wooden tongue depressor and ice. These assessments will evaluate light touch and cold sensation. The light touch assessment will be done first, followed by the cold sensation assessment. The tongue depressor application and ice application will be performed at predose (up to 15 min before block), 15 min (± 5 min), 30 min (± 5 min), 45 min (± 5 min), 1 h (± 15 min), 2 h (± 30 min), 8 h (± 30 min), 12 h (± 30 min), 24 h (± 1 h), 30 h (± 1 h), 48 h (± 1 h), 60 h (± 2 h), 72 h (± 2 h), 84 h (± 2 h), 96 h (± 3 h), 120 h (± 3 h), 144 h (± 3 h), and 168 h (± 3 h) from the end of the nerve block procedures, or until full sensory function has returned to predose levels in two consecutive evaluations. Each light touch

assessment will be rated independently. Each cold sensation assessment will be rated independently. Additional unscheduled assessments may be performed, particularly around the surgery, if no onset of block is noted on the last scheduled assessment prior to surgery. For each sensory assessment performed, all 4 locations (as described in Appendix 4, [Section 18.4](#)) will be assessed for both light touch and cold (e.g., total of 8 independent ratings will be performed for each sensory assessment).

Onset of sensory block (sciatic and saphenous nerve tracked independently) will be defined as the earliest timepoint with loss of light touch sensation and/or cold sensation along the distribution of the target nerve distal to the site of the block.

Offset of sensory block (sciatic and saphenous nerve tracked independently) will be defined as recovery of light touch sensation and/or cold sensation along the distribution of the target nerve distal to the site of the block on 2 consecutive assessments. After offset of all sensory assessments are noted (on 2 consecutive assessments for all 4 areas for both touch and cold sensation), no subsequent assessments will be conducted.

Duration of sensory block will be defined as the time between onset and offset of light touch sensory and/or cold sensation block for each nerve individually (see Appendix 4, [Section 18.4](#)).

Assessment of motor function (onset and offset of motor block):

- Motor function (onset and offset of motor block) will be assessed by voluntary active movement of the foot. This will be used to determine the onset and duration of motor blockade. The motor function test will be performed at predose (up to 15 min before block), 15 min (± 5 min), 30 min (± 5 min), 45 min (± 5 min), 1 h (± 15 min), 2 h (± 30 min), 8 h (± 30 min), 12 h (± 30 min), 24 h (± 1 h), 30 h (± 1 h), 48 h (± 1 h), 60 h (± 2 h), 72 h (± 2 h), 84 h (± 2 h), 96 h (± 3 h), 120 h (± 3 h), 144 h (± 3 h), and 168 h (± 3 h) from end of block procedure, or until full motor function has returned to predose levels in two consecutive evaluations. Additional unscheduled assessments may be performed, particularly around the surgery, if no onset of block is noted on the last scheduled assessment prior to surgery.

Onset of motor block (sciatic) will be defined as the earliest timepoint with partial or no foot movement.

Offset of motor block (sciatic) will be defined as resolution of the motor block with complete foot movement on two consecutive assessments. After offset of motor block is noted (on 2 consecutive assessments), no subsequent assessments will be conducted.

Duration of motor block will be defined as time between onset and offset of motor block (see Appendix 3, [Section 18.3](#)).

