6.3. Pharmacodynamic Assessments (Cohort 1 only)

Time of onset/offset is collected on the corresponding "PD Assessment – Onset/Offset Sensory/Motor Block" eCRF.

6.3.1. Assessment of Sensory Block:

Sensory function for the sciatic and saphenous nerve will be assessed independently using a wooden tongue depressor and ice. This assessment will evaluate light touch and cold sensation.

Sensory function assessment will include the following four locations:

- 1. Saphenous proximal Medial aspect of the lower leg (3-4 cm below the knee)
- 2. Saphenous distal Medial aspect of the lower leg (3-4 cm above ankle)
- 3. Sciatic proximal Lateral aspect of the lower leg (3-4 cm above ankle)
- 4. Sciatic distal Sole of the foot

The tongue depressor application and ice will be performed at predose, 15 min, 30 min, 45 min, 1 h, 2 h, 8 h, 12 h, 24 h, 30 h, 48 h, 60 h, 72 h, 84 h, 96 h, 120 h, 144 h, and 168 h hours from the end of the nerve block procedure, or until full sensory function has returned to baseline (preblock) levels in two consecutive evaluations. Additional unscheduled assessments may be performed, particularly around the surgery if no onset of block is noted on the last scheduled assessment prior to surgery.

Onset of sensory block (sciatic and saphenous nerve tracked independently) will be defined as the earliest timepoint with loss of EITHER light touch sensation OR cold sensation in EITHER proximal OR distal locations at any time. If onset time is not achieved, it will be considered censored at the last onset assessment time prior to surgery. **Offset of sensory block** (sciatic and saphenous nerve tracked independently) will be defined as recovery of BOTH light touch

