sensation AND cold sensation in BOTH proximal and distal locations on two consecutive recovery assessments (excluding Not Done assessment). After offset of all sensory assessments are noted (on 2 consecutive assessments for all 4 locations), no subsequent assessments will be conducted. If offset time is not achieved, it will be considered censored at the last offset assessment time after surgery. If the patient's sensory block is recovered at the last assessment to confirm, the sensory block is considered recovered at this last time point. **Duration of sensory block** will be defined as the time between onset and offset of the sensory blocks for each nerve individually. If onset is not achieved, duration will be calculated from the surgery start time through the offset time, left censored. If both onset and offset assessment time, interval censored. See Section 9.5.2.4 for how the censoring is handled in the analysis. If postdose onset assessments are completely missing, time to onset will be set to missing.

6.3.2. Assessment of Motor Block:

Motor function (onset and offset of motor block) will be assessed using the 2-point scale on the side of the block. This will be used to determine the onset and duration of motor blockade.

Motor function will be assessed using a 2-point scale. The motor function test will be performed at predose, 15 min, 30 min, 45 min, 1 h, 2 h, 8 h, 12 h, 24 h, 30 h, 48 h, 60 h, 72 h, 84 h, 96 h, 120 h, 144 h, and 168 h from end of block procedure, or until full motor function has returned to pre-dose levels in two consecutive evaluations. Additional unscheduled assessments may be performed, particularly around the surgery if no onset of block is noted on the last scheduled assessment prior to surgery.

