6.4. Change in the Study Design and Its Effect on the Statistical Analysis

Protocol version 1.0 (dated 28 July 2020) specified sensory function assessment by light touch. Six subjects enrolled under this version. Protocol Amendment 1 (dated 6 November 2020) adds cold sensation in the sensory function assessment. As such, six (6) subjects enrolled under Protocol v1.0 did not have cold sensation assessment. These 6 subjects will be excluded from the sensory block evaluation.

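### Sensory-block offset is defined differently in protocol 12.7 and SAP 6.3.1, and neither document says whether the analysed time is the eCRF entry or is derived from the ratings

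*Protocol*

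**What the plan says.** **Protocol 12.7.** Sensory onset for a nerve is the "earliest timepoint with loss of light touch sensation and/or cold sensation along the distribution of the target nerve". Offset is "recovery of light touch sensation and/or cold sensation along the distribution of the target nerve distal to the site of the block", confirmed at two assessments in a row. The definition of duration repeats and/or. The section does not say how many of a nerve's two locations must have recovered before offset is called. Testing stops only when all four areas have recovered for both touch and cold on two consecutive assessments.

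**SAP 6.3.1.** Onset is loss of either modality at either location. Offset takes in both modalities and both locations: after naming light touch, the definition goes on "sensation AND cold sensation in BOTH proximal and distal locations on two consecutive recovery assessments".

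**Source of the time.** SAP 6.3 opens with "Time of onset/offset is collected on the corresponding" PD onset/offset eCRF page. SAP 9.2.5 refers to censoring for cases where an onset or offset time was not captured.

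**Underlying data.** Protocol 12.7 and Appendix 4 call for eight ratings per assessment (four locations, two modalities), each recorded as YES or NO.

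**Use.** SAP 9.7.1 summarises duration of sensory block by nerve with Kaplan-Meier medians and quartiles. SAP 9.5 does not list it in the testing hierarchy.

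**Six early subjects.** SAP 6.4 notes that six subjects enrolled under protocol version 1.0 had no cold assessment: "These 6 subjects will be excluded from the sensory block evaluation".

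**The concern.** Each nerve has four ratings: two modalities at two locations. With *or*, the protocol wording lets a nerve be called recovered while one modality is still blocked. The SAP calls it recovered only when the last of the four ratings has returned. These are different quantities, and both would be reported under the same name.

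SAP 9.1 says the SAP's statistical methods supersede those in the protocol. That settles which definition the analysis intends. It does not settle which number the analysis reads. Site staff work from the protocol. If the time they enter on the onset/offset page goes straight into the Kaplan-Meier summary, the report could cite the SAP definition over times recorded under a different one, and sites could differ in how they read and/or. Duration of sensory block is a named PD endpoint and would be reported for all three arms.

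**Working it through.** The plan states no figure for this endpoint, so there is none to reproduce. The check sets the definitions side by side and then sizes the gap.

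**1. Definitions**

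| | Protocol 12.7 | SAP 6.3.1 | Compatible? |
|---|---|---|---|
| Onset, modality | touch and/or cold lost | either lost | Yes |
| Onset, location | not specified | either | Yes |
| Offset, modality | touch and/or cold recovered | both recovered | Only if and/or means *and* |
| Offset, location | number not stated | both | Not settled by the protocol |
| Assessment that dates offset | not stated | not stated for sensory; first of the two for motor (6.3.2) | Open in both |

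**2. What one visit of lag is worth.** The scheduled PD visits from 8 h are 8, 12, 24, 30, 48, 60, 72, 84, 96, 120, 144 and 168 h (protocol Table 2). The successive gaps are 4, 12, 6, 18, 12, 12, 12, 12, 24, 24 and 24 h, with a median of 12 h. If the deciding rating recovers one visit later under one rule than under the other, offset moves by 4 to 24 h. This needs no assumption about the drug. Dating offset at the second instead of the first of two consecutive scheduled assessments costs a gap of the same size.

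**3. Illustration with assumed recovery times.** The documents give no recovery data, so all inputs in this step are assumptions. For modality *j* and location *k* of one nerve, the recovery time is

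T_jk = m × exp(0.4 Z + w e_jk),

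with Z and e_jk standard normal, m = 24 or 48 h, between-subject log SD 0.4 and within-subject log SD w. Each time is rounded up to the next scheduled visit. The rules compared are:

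- Either modality, both locations: offset = min over *j* of (max over *k* of T_jk), that is, the first modality to have recovered at both locations.
- SAP: offset = max of all four T_jk.

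| m (h) | w | Median, either modality (h) | Median, SAP rule (h) | Shift (h) | Subjects with a different offset visit |
|---|---|---|---|---|---|
| 24 | 0.2 | 30 | 30 | 0 | about 42% |
| 24 | 0.3 | 30 | 48 | 18 | about 56% |
| 24 | 0.4 | 30 | 48 | 18 | about 66% |
| 48 | 0.2 | 60 | 60 | 0 | about 58% |
| 48 | 0.3 | 60 | 72 | 12 | about 71% |
| 48 | 0.4 | 60 | 84 | 24 | about 78% |

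**4. Sensitivity.** With w = 0.05 to 0.1, 12% to 36% of subjects change and the medians agree. With w = 0, the four ratings recover together and the rules coincide. A second set of assumptions (median 24, 48 or 72 h; log SD 0.3 or 0.5; correlation between ratings from 0 to 1) gives a median shift of 0 to 36 h, with 0% to 87% of subjects changing. If and/or is read as *and*, with both locations required, the protocol and SAP rules are the same and the shift is zero.

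**The case against.** The strongest reply is that the SAP already has an explicit rule, takes precedence, and is written at the level of individual ratings. It counts consecutive recovery assessments, skips those marked Not Done, covers recovery first seen at the last assessment, and tabulates sensation by time point (Table 4 and 9.7.1). That suggests derivation from the ratings. The ratings should also exist, because testing continues until all four areas have recovered for both modalities. All of this stands, and it is why the remedy needs no new data. It does not close the gap: no sentence says the time is derived, while SAP 6.3 and 9.2.5 both treat it as a collected item.

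A reader might infer that the reported durations do depend on each site's rule, or that the medians will be wrong. The documents do not support that. The eCRF is not among them, and they do not say that sites judge the composite offset or that the entry is analysed unchecked.

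A reader might also compare the first of four ratings to recover with the last. Under the same assumptions that gives medians of 24 against 30/48/48 h and 48 against 60/72/84 h, with 73% to 98% of subjects changing. This is the most extreme reading. The and/or concerns modality, and nothing in protocol 12.7 says recovery at one location is enough.

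The exclusion in SAP 6.4 is not an error. It is prespecified with its reason, since a two-modality rule cannot be applied without cold data. Six of about 60 would be 10% of Cohort 1, with standard errors wider by √(60/54) = 1.05, but only if all six were in Cohort 1. The SAP does not say so, and the cohorts enrol in parallel.

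**Conclusion.** The point holds in a limited form. The offset definitions conflict unless and/or is read as *and* with both locations required, and the source of the analysed time is unstated. The reported sensory-block duration may therefore not follow the SAP definition, on condition that the eCRF time is analysed as entered.

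The schedule alone makes each visit of lag worth 4 to 24 h. The 42% to 78% of subjects affected and the 0 to 24 h shift in the median rest on the assumed log-normal recovery times with w from 0.2 to 0.4. They show what is possible and do not predict this trial.

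The consequence is contained. Sensory duration is a descriptive Cohort 1 PD summary outside the testing hierarchy. Onset agrees between the documents. Motor-block duration, which is tested, uses one two-point scale and has no such modality conflict. The correction is worth making because it is cheap and removes the doubt entirely.

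**What to change.** - **SAP 6.3.1:** state that sensory onset and offset are derived by program from the eight recorded YES/NO ratings using the SAP rule, with offset dated at the first of the two consecutive recovery assessments, as for motor block. Use the eCRF onset/offset entry only as a consistency check, and list discrepancies.
- **Protocol 12.7:** replace and/or with the SAP wording in the onset, offset and duration definitions (either modality for onset, both for offset, with the locations stated). SAP sections 5 and 6.4 show that enrolment had begun, so this cannot change times already entered. The SAP sentence is the change that protects the analysis.
- **Optional, SAP 6.4:** add a light-touch-only summary of onset and duration that keeps those of the six version 1.0 subjects who were in Cohort 1, and exclude them only from the combined touch-and-cold endpoint.

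The cost is a few sentences of SAP text, a protocol clarification, one derivation program with a discrepancy listing, and one extra PD table if the optional summary is added. No new data are needed.
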